11.7.3. Demographic and Other Baseline Characteristics

Demographic and baseline condition related characteristics will be tabulated and compared between the study groups by data type, this data will also be compared between US and OUS sites for poolability confirmation. Continuous variables will be summarized by a mean, standard deviation, minimum, median and maximum and categorical variables by a count and percentage.

These data will include:

- Demographic data

- Medical history
- Type of pain medications/treatments used for migraine as well as rescue
- Other concomitant medication
- Migraine attacks characteristics
- Physical examination

11.7.4. Disposition of Subjects

The number of subjects who entered the study and completed each stage of the study will be provided, as well as the reasons for all post randomization discontinuations, grouped by major reason, e.g., lost to follow-up, adverse event, poor compliance, did not administer any treatment (with reasons). A list of discontinued patients, protocol deviations and subjects excluded from the performance analysis will be provided as well.

11.7.5. Efficacy Analysis

Primary Efficacy Analyses

The primary endpoint is the proportion (%) of patients reporting reduction in their pain level 2 hours post-treatment without rescue medications from severe or moderate to mild or no pain, or from mild to no pain, in their first treated eligible (per **Section 9.1.6**) migraine attack (excluding the "self-practice" treatment). A count and percentage of subjects reporting such headache pain reduction without rescue medications will be calculated and presented for both study groups, each with a two-sided 95% exact confidence interval. The groups will be compared with a chi-squared test and a Fisher's exact test.

If the null hypothesis is rejected in favor of the alternative hypothesis and the proportion (%) of subjects responding to this endpoint in the active group is greater than that of the sham group, the study will be deemed successful.

The primary endpoint will also be evaluated stratified by center using a Mantel-Haenszel test to assess the center by group interaction.

A sensitivity analysis of the primary end-point will be performed to assess the impact of missing data on the study outcome. This will be performed using several possible imputation methods.

Subset Analyses of Primary Endpoint

Adjustment for other covariates such as demographics or other baseline patient characteristics may be performed by adding these variables into a logistic regression model.

Subgroup analysis will be performed and reported by adding the variables listed below to a logistic regression model:

- use of migraine medications
- blinding assessment
- US vs. OUS sites

Secondary Efficacy Analyses

The secondary efficacy variables will be summarized by a count and percentage and compared with a chi-squared test and a Fisher's exact test.

Exploratory Analyses

The exploratory variables will be summarized by a count and percentage and compared with a chi-squared test and a Fisher's exact test.

Global Impression of Effect will also be summarized by descriptive statistics per treatment group and compared between the groups with a t-test.

Frequency of use of rescue medications will be summarized by descriptive statistics per treatment group and compared between the groups with a t-test.

Safety Analysis

The primary safety variable, the cumulative incidence (and 95% CI) of device related adverse events (AEs) throughout the study, will be presented in tabular format and will include incidence tables by severity.

Adverse event rates will be compared between the study groups with a Fisher's exact test.

Serious adverse events will be listed and discussed individually.

Treatment tolerability will be compared between the study groups. The number and percent of subjects who fail to complete the study and the number and percent of subjects who fail to complete the study because of Adverse Events will be presented as well.

Handling of Missing Data

Multiple imputation for binary data will be used as the primary imputation method in the case of missing data for the primary efficacy end-point.

Additional sensitivity analysis of the primary end-point will be performed to assess the impact of missing data on the study outcome using possible imputation methods for binary data:

 Neurolief Brain Innovation	THE RIME STUDY: ABRIDGED CLINICAL INVESTIGATION PLAN	Doc No.: CL-CIP-001 Abridged Ref Rev: REV.2 / 11JUN2019 Pg. 39 of 41
--	---	---

Observed Data: Use only subjects with non-missing pain data and who did not withdraw early from study

Dropout/AE Imputation: A subject with no post baseline measurement of pain or a subject withdrawn due to an adverse event or treatment intolerance should be considered as a nonresponder for this analysis.

Best Case Scenario: Assume all visits with missing pain data in active group are successes. Assume all subjects in the sham group with missing pain data are failures.

Worst Case Scenario: Assume all visits with missing pain data in active group are failures. Assume all subjects in the sham group with missing data are successes.

Imputation of missing data may be performed on secondary and exploratory endpoints as well.

Pooling

Subgroup analysis of the primary efficacy endpoint by center, and US vs OUS, will be used to evaluate the poolability of the results. The significance of center-to-center variability in treatment effect will be evaluated by including an interaction term of treatment group by center in a logistic regression model. In the case that poolability is questionable, the reasons for differential treatment effect, such as subject and clinical characteristics, will be investigated and reported.

12. References

2. See, World Health Organization, Headache Disorders, available at <http://www.who.int/mediaacentre/factsheets/fs277/en/>.

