11.5. Randomization

Upon completion of the run-in period, eligible subjects will be randomly allocated (with a 1:1 ratio) to one of the following 2 treatment groups based on a randomization scheme using the permuted block method stratified by center:

- Group A – active (Relivion™) stimulation
- Group B = sham stimulation

The randomization scheme will be prepared by the study statistician using the SAS (version 9.4.) random number procedure. The block size will be random, and all study personnel will be therefore blinded to the randomization block size.

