11.7.2. Significance Level and Handling of Type I Error

Type I Error

The overall significance level for this study is 5% using two-tailed tests, except for treatment by site interaction that will be tested at a significance level of 10%.

Hierarchy Approach for Secondary Endpoint Analysis

The hierarchy approach will be adopted for the primary and secondary endpoints to control type I error due to multiple endpoint testing. Thus, the primary endpoint will first be tested and only if $p < 0.05$, will the secondary endpoints be tested. For the three secondary performance endpoints, the Benjamini–Hochberg step-up method will be used to adjust the p-values.

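### The center-stratified Mantel-Haenszel test is given an interaction question it cannot answer, while the deciding test leaves out the randomization stratum

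*Protocol*

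**What the plan says.** Protocol 11.5 allocates subjects 1:1 by a "randomization scheme using the permuted block method stratified by center". For the primary endpoint, Protocol 11.7.5 then says "The groups will be compared with a chi-squared test and a" Fisher's exact test. Neither uses center, and study success follows from rejecting the null hypothesis in favor of active.

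The same section adds a second analysis: "The primary endpoint will also be evaluated stratified by center using a Mantel-Haenszel test to assess the center by group interaction".

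The Pooling paragraph of 11.7.5 handles variation between centers separately, by "including an interaction term of treatment group by center in a logistic regression model", and also looks at US versus OUS subgroups. Protocol 11.7.2 sets 5% for all tests "except for treatment by site interaction that will be tested at a significance level of 10" percent.

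The SAP prevails where it differs from the protocol. Its public, abridged text covers endpoints and analysis sets and names no test for the primary endpoint, so the protocol wording is the only visible statement.

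**The concern.** Two separate things look wrong.

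- **A test with the wrong purpose.** The Mantel-Haenszel test combines the within-center differences into one overall treatment comparison. It responds to the average effect and is nearly blind to effects that differ between centers. Taken literally at the 10% level, it would tend to signal interaction when the device works equally well everywhere, and to stay silent when effects in different centers cancel out.
- **A deciding test that ignores the design.** Permuted blocks within center balance the arms inside each center. If response levels differ between centers, the pooled test counts that variation as error although the design has removed it from the comparison. The price is power. That matters more here because the SAP Introduction reports only 109 subjects with primary endpoint data, against 180 evaluable planned.

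**Working it through.** **Inputs from the documents.** 45% versus 25%, two-sided 5%, 80% power, 180 evaluable and 200 randomized (Protocol 11.3); at most 12 sites, about 33% of subjects from the US (Protocol 6.1); about 130 enrolled for efficacy, 109 with primary data (SAP Introduction).

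**Step 1: the plan's own figure.** n per arm = [1.960 × √(2 × 0.35 × 0.65) + 0.842 × √(0.45 × 0.55 + 0.25 × 0.75)]² / 0.20² = (1.322 + 0.555)² / 0.04 ≈ 88.1, so 89 per arm, or 178 against the stated 180. Power at 90 per arm is 80.8%, and 180 / 0.9 = 200. The sample size is sound for the pooled test. At 109 subjects (54.5 per arm) the same formula gives 59.3%.

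**Step 2: what the Mantel-Haenszel test detects.** The statistic is z = Σ(aₖ − Eₖ) / √ΣVₖ over centers k, where aₖ is the number of active responders and Eₖ its expectation given the center's totals. Assume 6 centers with 15 per arm.

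- *Reversed effects*, 50% versus 20% in three centers and 20% versus 50% in the other three. Expected active responders are 7.5 or 3.0 and Eₖ = 10.5/2 = 5.25, so the deviations are +2.25 three times and −2.25 three times. They sum to 0: interaction is extreme and the expected numerator is zero.
- *Same effect everywhere*, 45% versus 25%. Each deviation is 6.75 − 5.25 = +1.5, total 9. Vₖ = 15 × 15 × 10.5 × 19.5 / (30² × 29) = 1.765, total 10.59. So z ≈ 9/3.25 = 2.77, although there is no interaction.

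Simulation (3,000 runs each) agrees. With reversed effects, Mantel-Haenszel gave p < 0.10 in 8% of runs and Breslow-Day in 95%. With the uniform effect, the figures were 88% and 11%.

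**Step 3: can a full center interaction be fitted?** With 12 sites, 109/12 = 9.1 and 130/12 = 10.8 subjects per site on average, over four treatment-by-outcome cells, for an interaction with 11 degrees of freedom. In simulation at n = 109, at least one center had an empty cell in over 99% of runs with 12 sites and in 74–85% with 8 equal sites. Breslow-Day does not escape this: with 12 unequal sites and a uniform effect it rejected in 16.6% of 2,000 runs at a nominal 10%.

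**Step 4: effect of stratifying the deciding test.** The pooled variance uses p̄(1 − p̄), which equals the average within-center variance plus the between-center variance of the rates. Under within-center balance only the first part affects the comparison, so the pooled test is conservative. Simulated power (%), with true marginal rates of 45% and 25%:

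| Analyzed n, assumed sites | Logit SD | Chi-squared | Stratified | Difference |
|---|---|---|---|---|
| 109, 12 unequal | 0 | 60.0 | 58.3 | −1.7 |
| | 0.5 | 58.9 | 59.0 | +0.1 |
| | 1.0 | 59.9 | 64.3 | +4.4 |
| 130, 12 unequal | 0 | 68.3 | 67.2 | −1.1 |
| | 0.5 | 67.9 | 68.7 | +0.8 |
| | 1.0 | 69.3 | 74.5 | +5.2 |
| 108, 9 equal | 0 | 60.2 | 59.6 | −0.6 |
| | 0.5 | 60.4 | 61.9 | +1.5 |
| | 1.0 | 60.6 | 66.6 | +6.0 |

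These use 4,000, 8,000 and 20,000 runs per cell respectively, so the Monte Carlo error of one power figure is at most √(0.6 × 0.4/4,000) = 0.8 points. A repeat at n = 109 gave −2.0 at SD 0. At n = 109 the type I error of the pooled test was 4.9%, 4.4% and 3.4% at SD 0, 0.5 and 1.0. The stratified test stayed near 5% (in the 9-center layout, 5.2%, 5.3% and 4.9%).

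**What the SDs mean.** Around a 25% sham rate (logit −1.099), ±2 SD covers site rates of about 11% to 48% at SD 0.5 and 4% to 71% at SD 1.0.

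**The case against.** The strongest reply is that little is actually missing. A reader might infer that the plan has no usable interaction test; the documents do not support that. The Pooling paragraph specifies one, 11.7.2 gives its level, and poolability is judged from that term and the subgroup analyses, so a Mantel-Haenszel p-value need not be read as evidence for or against pooling. A reader might also infer that ignoring the stratum endangers type I error. It does not: a significant pooled result remains valid.

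It is also fair that the pooled chi-squared test matches the sample-size calculation, that the center-stratified result will be produced anyway, and that the power gain needs large site differences for which the documents give no evidence. Site number, site sizes, block sizes and between-site SD are all assumptions. At n = 109 the 12-site runs show essentially no gain at SD 0.5 and a loss of about 2 points at SD 0.

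Finally, the public SAP is abridged and the full one may name a different primary test. Nobody can conclude from the public text that the final analysis was uncorrected.

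What remains after all this is the wrongly stated purpose, the fragility of the planned center interaction, and a low-cost improvement to the deciding test.

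**Conclusion.** The stated purpose of the Mantel-Haenszel test is wrong, and this needs no assumption about sites. Its practical harm is limited because a valid type of interaction test is planned alongside it, though that test may not be estimable if the analyzed subjects are spread over 12 sites.

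Leaving center out of the deciding test is a choice that can cost efficiency, not an error that invalidates the result. Under the assumed layouts at 108 to 130 subjects, stratifying changes power by about −2 to −0.6 points with no site differences, 0 to +1.5 points at a logit SD of 0.5, and +4 to +6 points at SD 1.0. With power near 60% at 109 subjects if the planned effect is true, the change is worth making, but it does not restore the planned 80%.

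**What to change.** 1. In Protocol 11.7.5, or in the SAP that governs it, describe the Mantel-Haenszel test as the center-adjusted test of the treatment effect and delete the interaction purpose.
2. Before unblinding, name the center-stratified Cochran-Mantel-Haenszel test as the single deciding test, reported with the stratified risk difference. Keep the pooled chi-squared and Fisher tests as supportive. This also settles which test decides, since the protocol now names two.
3. Fix, blind to treatment, a rule for pooling within country those centers too small to contribute, for example those without both arms.
4. Assess interaction with one treatment-by-region (US versus OUS) term at the 10% level, not with Breslow-Day across sparse centers. State that non-significance does not show that the effects are equal. If 33% of 109 are from the US (about 36 against 73), the standard error of the difference between regional risk differences is about √(0.435/18 + 0.435/36.5) = 0.19, where 0.435 = 0.45 × 0.55 + 0.25 × 0.75. Only a gap of about (1.645 + 0.842) × 0.19 = 0.47 would be found with 80% power. Show the regional estimates with confidence intervals.

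The cost is a few sentences while the data are still blinded, as the SAP Introduction reports they are, and up to about 2 points of power if sites do not differ. If unblinding has already taken place, the deciding test should stay as it was specified, with the stratified result shown beside it.

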Refer to **Figure 1** for a summary of the study schedule of assessment. Specifically, subjects will be evaluated at Visit 1 to assess whether they meet study eligibility criteria. Those meeting all of the inclusion and none of the exclusion criteria will initiate the Run-In Period for 28 days (+10 days). Subjects will return for Visit 2 (Day 0) for a repeat assessment of eligibility. Those found eligible will be enrolled and randomized. A subject is considered enrolled in the study when it is determined that all inclusion/exclusion criteria are met during visit 2 and after run-in period diary is assessed. At this point they will undergo device, device app and Patient Reported Outcome (PRO) training and will be asked to complete the blinding assessment. Subjects will be sent home with the device and the study dedicated smartphone for a 2 weeks Self-Practice Period. During these 2 weeks they will perform 2 self-training treatment sessions, not during a Migraine attack and complete the PRO. Device logs will be verified by the study team during Visit 3 (potentially remote verification). Subjects with at least 1 self-training session completed successfully will be approved by site team to initiate the Treatment Period and to treat at least 1 and up to 5 migraine episodes, within up to 70+10 days from visit 1, whichever comes first. Once completing the Treatment Period, they will return for end of study visit (Visit 4) during which the device will be returned, final data will be collected and the subjects will be exited from the study.

Subjects found ineligible by the procedures required at screening will be marked as 'screen failure' on the screening & enrollment log and will not take part in the study. Screen failure subjects will not be included in the intention-to-treat analysis, nor will they be counted as part of the target subject sample number.

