8.1.2. Run-In Period (Day 0 -28+10 days)

- Completion of the Run-In Diary by the subject during the run-in period. A Subject who failed to complete the required information on the Run-In Diary will be considered a screen failure. The diary will capture information with respect to frequency, intensity and duration of migraine episodes, existence of aura and other symptoms, use of rescue medications, and other types of headaches. Two (2) different Migraine episodes will be defined by, at minimum, by 48 hours free of pain in between.
- Study team may contact the subject periodically to remind him/her to fill in the diary

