8.2. Prior and Concomitant Medications

During the Run-In and Self-Practice Periods, the subject will use prophylactic medications as prescribed and rescue medications as needed and will document their use in the Migraine Diary.

 Neurolief Brain Innovation	THE RIME STUDY: ABRIDGED CLINICAL INVESTIGATION PLAN	Doc No.: CL-CIP-001 Abridged Ref Rev: REV.2 / 11JUN2019 Pg. 28 of 41
--	---	---

During the Treatment Period, the subject will continue his/her prophylactic medications and rescue medications as needed. While using the Relivion™ the subject will be asked to refrain from taking rescue medications/cannabis in the 4 hours prior to and 2 hours following each treatment.

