8.5. Medication Compliance

While using the Relivion™ the subject will be asked to refrain from taking rescue medications/cannabis in the 4 hours prior to and 2 hours following each treatment. Subject will ascertain he/she did not consume any rescue medications/cannabis in the 4 hours prior to study treatment initiation. During each study treatment and up to 24 hours afterwards subjects will document any rescue medication/cannabis intake. PRO data of subjects who consumed rescue medications/cannabis will not be considered for the analysis of the related treatment time point.

 Neurolief Brain Innovation	THE RIME STUDY: ABRIDGED CLINICAL INVESTIGATION PLAN	Doc No.: CL-CIP-001 Abridged Ref Rev: REV.2 / 11JUN2019 Pg. 29 of 41
--	---	---

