11.7. Statistical Analysis

11.7.1. General Considerations

Statistical analyses will be performed using SAS® v9.4 (SAS Institute, Cary NC, USA). Statistical analyses and reporting will be performed in compliance with FDA Guidance E6 GCP, 21 CFR part 812, E9 and ISO 14155.

All statistical tests will be two-sided. The required significance level of findings will be equal to or lower than 5%, nominal p-values will be presented. Where confidence limits are appropriate, the confidence level will be 95%.

Continuous variables will be summarized by a mean, standard deviation, minimum, median and maximum and categorical variables by a count and percentage. For comparison of means (continuous variables), the two-sample t-test or the Wilcoxon rank sum test will be used as appropriate. For comparison of proportions (categorical variables), the chi-squared test or Fisher's exact test will be used as appropriate.

If multiple measurements are taken in a single patient, statistics described below will be appropriately modified to accommodate the within patient correlation.

Deviations from the planned analysis will be described, with proper justification, in the clinical study report.

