Secondary efficacy endpoints include:

1. Proportion of subjects reporting improvement in their most bothersome migraine-associated symptom (MBS) other than a headache, 2 hours post-treatment initiation (if rescue therapy was not used), in their first eligible

treated migraine attack. MBS may be nausea, photophobia, phonophobia as defined by each subject prior to beginning of the treatment.

2. Proportion of subjects reporting reduction of migraine headache pain 1-hour post treatment initiation (if rescue therapy was not used), from severe or moderate to mild or no pain, or from mild to no pain, in their first eligible treated migraine attack.
3. Proportion of subjects who are pain free at 2 hours post treatment initiation (if rescue therapy was not used), in their first eligible treated migraine attack.

2.3

Additional efficacy endpoints

1. Proportion of subjects reporting freedom from their MBS other than a headache, 2 hours post-treatment initiation (if rescue therapy was not used), in their first eligible treated migraine attack.
2. Proportion of subjects who are pain free at 1-hour post treatment initiation (if rescue therapy was not used), in their first eligible treated migraine attack.
3. Proportion of subjects rating the subjects positive (score of 4 or 5) Global Impression of Effect of study device at the end of the study, defined as satisfied or very satisfied using a simple Likert-type scale whereas 1 = Very dissatisfied, 2 = dissatisfied, 3 = unsure, 4 = satisfied, 5 = Very satisfied.
4. Proportion of subjects reporting 2-24h headache relief, defined as headache relief at 2 hours without rescue medications, then no moderate to severe headache in the next 22 hours, and no use of rescue medication or additional stimulation.

Additional efficacy analyses that will be performed

1. Proportion of subjects reporting improvement in their MBS other than a headache AND reduction in their pain level, 1 and 2 hours post-treatment initiation (if rescue therapy was not used), in their first eligible treated migraine attack.
2. Proportion of subjects reporting freedom from their MBS other than a headache AND pain free, 1 and 2 hours post-treatment initiation (if rescue therapy was not used), in their first eligible treated migraine attack.
3. Rescue medicine usage.
4. Proportion of subjects who had pain relief in at least 50% of their eligible treated attacks at each timepoint.

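### The exploratory comparison of rescue-medication frequency ignores each subject's run-in rescue use, giving up some precision; the t-test is valid and the primary conclusion is unaffected

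*Protocol*

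**What the plan says.** Under Exploratory Analyses, Protocol 11.7.5 states: "Frequency of use of rescue medications will be summarized by descriptive statistics per treatment group and compared between the groups with a t-test". Section 11.7.1 shows which test is meant: "For comparison of means (continuous variables), the two-sample t-test or the Wilcoxon rank sum test will be used as appropriate". Neither option takes a covariate.

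The same behaviour is recorded before randomization. By 8.1.2 the run-in diary captures, among other items, "existence of aura and other symptoms, use of rescue medications, and other types of headaches", and the diary is a condition of entry: "A Subject who failed to complete the required information on the Run-In Diary will be considered a screen failure". Section 8.2 says that during run-in and self-practice subjects take "rescue medications as needed and will document their use in the Migraine Diary". In the treatment period, 8.5 says: "During each study treatment and up to 24 hours afterwards subjects will document any rescue medication/cannabis intake".

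The SAP prevails where the two documents differ. Its section 2.3 lists "Rescue medicine usage" as item 3 of the additional efficacy analyses and gives no method, so the protocol's t-test is the only method stated.

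Nothing else supplies the adjustment:

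- The covariate text in 11.7.5 concerns logistic models for the primary endpoint.
- Section 11.7.3 tabulates and compares baseline characteristics, including the type of medication used. That can reveal an imbalance but does not correct for it.
- The clause in 11.7.1 on repeated measurements deals with within-patient correlation, not with baseline.

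**The concern.** If a subject's rescue use before randomization predicts use afterwards, an analysis that leaves it out carries that between-subject variation in its error term. The data are already collected and should be nearly complete in randomized subjects, so the precision costs almost nothing.

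It matters more in a trial that stopped short. SAP section 1 reports about 130 subjects enrolled for efficacy and 109 with primary-endpoint data, against 180 evaluable planned. A chance difference between arms in prior rescue use also tends to be larger in a smaller trial, and an unadjusted comparison attributes part of it to the device.

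The outcome's unit is open as well. The protocol does not say whether frequency is counted per attack, per 24 hours or per period, while subjects treat between 1 and 5 attacks (8.1.6). If a raw count is meant, it mixes the tendency to take rescue with the number of attacks treated.

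**Working it through.** **Inputs.** From the documents: two-sided 5% level, 80% power and 90 per arm (11.3, 11.7.1); 1:1 allocation (11.5); 109 and about 130 subjects (SAP section 1). No SD, effect size, power or correlation is given for rescue frequency. Assumed: rho from 0.2 to 0.7, and an equal split at the achieved sample sizes. Results are in SD units under the normal approximation.

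**1. The plan's own figure (primary endpoint, 45% vs 25%).** n per arm = [1.96·√(2·0.35·0.65) + 0.842·√(0.45·0.55 + 0.25·0.75)]² / 0.20² = 88.1, so 89 per arm or 178 in total, against 180 stated. Power at 90 per arm is 80.8%, and 180/0.90 = 200. The figure is reproduced, but it says nothing about rescue use.

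**2. Unadjusted detectable difference.** d = (1.96 + 0.842)·√(2/m), with m per arm. This is 0.418 SD at m = 90 and 0.537 SD at m = 54.5 (N = 109).

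**3. Gain from adjustment.** With run-in use as a linear covariate, the residual variance is multiplied by 1 − rho². The interval narrows by 1 − √(1 − rho²). Power of 80% becomes Φ(2.802/√(1 − rho²) − 1.96) at any N. The equivalent unadjusted sample size is N/(1 − rho²).

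| Assumed rho | 1 − rho² | Interval narrower by | 80% power becomes | N = 109 acts like | N = 180 acts like |
|---|---|---|---|---|---|
| 0.2 | 0.96 | 2.0% | 81.6% | 114 | 188 |
| 0.3 | 0.91 | 4.6% | 83.6% | 120 | 198 |
| 0.5 | 0.75 | 13.4% | 89.9% | 145 | 240 |
| 0.7 | 0.51 | 28.6% | 97.5% | 214 | 353 |

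A gain of at least five percentage points needs rho of about 0.36 or more.

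**4. Effect of the early stop.** Take d = 0.418 and power = Φ(d·√N / (2√(1 − rho²)) − 1.96). At N = 130, power is 66% unadjusted and 79% at rho 0.5. At N = 109 it is 59% and 71%.

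**5. Chance imbalance.** The baseline difference between arms has SD √(2/m): 0.149 at N = 180 (95% range ±0.29) and 0.192 at N = 109 (±0.375). An imbalance of 0.3 SD moves the unadjusted estimate by 0.3·rho, which is 0.06, 0.09, 0.15 or 0.21 SD. Given that imbalance, the two-sided error of the unadjusted test is about 6%, 6.5%, 9% or 11% at N = 109, and 6%, 8%, 14% or 22% at N = 180. Averaged over all randomizations it is 5%.

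**6. Which rho is plausible.** Suppose both periods are measured as the share of attacks with rescue, with run-in attacks uniform on 1–6 (mean of 1/n = 0.408), treated attacks uniform on 1–5 (0.457), and the same personal propensity in both. With within-subject correlation c between attacks, rho = c / √{[c + (1 − c)·0.408]·[c + (1 − c)·0.457]}. For c = 0.1, 0.2 and 0.3 this gives 0.20, 0.37 and 0.50. If the propensities in the two periods correlate only 0.7 (an assumption), these become 0.14, 0.26 and 0.35, all below the five-point threshold.

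**The case against.** A reader might infer that the t-test is biased or has the wrong error rate, or that a baseline imbalance goes straight into the result. The documents do not support this. In a 1:1 randomized comparison the test is unbiased and holds 5% over randomizations, its standard error already allows for chance imbalance, and an imbalance passes through only in proportion to rho.

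A reader might also infer a threat to the trial's conclusion. There is none. Rescue frequency is not one of the four listed exploratory endpoints, it lies outside the testing hierarchy in 11.7.2, and no passage plans a claim on it.

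The size of the gain is open to fair challenge. Nothing in the documents shows that rescue use is a stable habit. It is taken as needed in run-in, whereas around treated attacks subjects are asked to refrain (8.1.6, 8.2, 8.5), and some attacks are not to be treated at all. Treatment-period recording includes cannabis, which 8.1.2 does not mention. All of this lowers rho. The 80% starting power is a yardstick, not a plan figure, and the figures at 130 may not apply, since efficacy uses only subjects with an eligible treated attack.

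Two more points stand. The diary is not said to link rescue use to individual attacks, so a run-in share of attacks may not be derivable. The SAP is abridged, and a fuller version may name a method. These points limit the weight of the concern, but none supplies the missing adjustment.

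**Conclusion.** The point holds as a modest loss of efficiency. The only stated method for rescue frequency is unadjusted, although the relevant baseline is collected in every subject as a condition of entry. The gain forgone ranges from negligible (rho 0.2: interval 2% narrower, power 80% to about 82%) to substantial (rho 0.7: 29% and 97.5%), with 13% and 90% at rho 0.5. The documents do not settle where in that range the trial lies, and the request to refrain from rescue favours the lower part. It is worth doing because it is cheap. The analysis as planned is not wrong, and success on the primary endpoint does not depend on it.

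**What to change.** In Protocol 11.7.5, and as the stated method for item 3 of the additional analyses in SAP 2.3:

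- Define the outcome relative to the number of treated attacks, for example the share of treated attacks with rescue, or a count with treated attacks as the denominator.
- Compare arms with a linear model (ANCOVA), or a count or binomial model, containing arm and the subject's run-in rescue use as recorded in the diary, for example as a rate over the run-in period. If the diary links rescue use to each attack, the run-in share of attacks with rescue may be the covariate instead.
- Keep the unadjusted group summaries as description.

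The cost is one derived covariate and a stated rule for subjects with no run-in attack, for whom a share is undefined and a rate is zero for lack of occasion. No new data are needed. The SAP says the data were still blinded and unanalysed when it was written, so the model could be specified there without knowledge of results.
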